1.1.2 Interventions

In the 1970ies it became clear that T1D is an autoimmune disease and therefore immune interventions were tried. We performed the first immune intervention studies in the world on diabetic children when we already 30 years ago used plasmapheresis in newly-diagnosed children and adolescents with some positive effects (13). As a side effect of that treatment a new protein with the weight 64kD was found in plasma (14), which later showed to be Glutamic Acid Decarboxylase (GAD). The breakthrough, taken as a proof for the concept of immune intervention, was cyclosporin, which doubtlessly slowed down the autoimmune destructive process and gave improved residual insulin secretion, while other trials with immune suppression had minimal effect, especially so in children (15, 16, 17), or showed too serious adverse events or risks (18, 19). In an effort to modulate the immune system we used photopheresis. Although clear effects on the immune system were demonstrated in a double blind placebo-controlled trial (20), the clinical effect was minimal and almost no improvement of residual beta cell function could be seen (21). Thus, with no successful immune intervention, our interest was directed to protective agents such as Nicotinamide and Diazoxide, with no or transient effect (22, 23, 24). With increasing knowledge of the immune process leading to beta cell destruction, it has become possible to direct more precisely the immune intervention to target the important T-cells. Promising studies using anti-CD3 antibodies in an attempt to block the destructive immune process have been performed. Result from both North-American and French trials with anti-CD3 have shown that it is possible to block the destructive autoimmune process and thereby at least postpone the decline of the beta cell function (25,26). The decline of residual insulin secretion was significantly slowed down, but unfortunately it looks as if the decline was just delayed a year, and thereafter the declining C-peptide curve went parallel to the declining curve in the placebo group. Furthermore, a majority of the patients experience some Cytokine Release Syndrome (CRS), which may be quite serious, and in addition a number of side effects were seen in most of the patients. We have participated in one of two recent Phase III trials (Macrogenics trial), which failed to reach the primary endpoint, although the arm with the most intense treatment indeed showed some preservation of residual insulin secretion and lower exogenous insulin requirement to reach good HbA1c (27). New studies are needed but it is difficult to believe that this type of treatment alone will be the accepted solution for general clinical use. Even less likely is such a treatment accepted as a preventive treatment in otherwise healthy individuals of whom many never would develop diabetes.

1.1.3 Immune therapy with auto-antigens

In the treatment of allergic diseases, immunotherapy with small amount of disease specific antigen has been efficiently used during many years. The mechanism for this treatment remains unclear, although modulation of the immune responses and induction of regulatory cells have been suggested. In autoimmune diseases no such treatment has been successful, but should be tried (28). Experiments in diabetes prone animals have shown that treatment with a heat shock protein could delay or postpone development of diabetes. The use of Diapep277 peptide in a

study in adults showed significant preservation of insulin secretion without almost any adverse events (29). Later trials in children and adolescents with T1D (30), however, have shown no effect. Studies with Diapep277 treatment in so called LADA (Latent Autoimmune Diabetes in the Adult) are ongoing, and preliminary results (reported at IDF, Dubai dec 2011 and at ADA June 2012) suggests that treatment with Diapep277 may preserve beta cell function in adults with mild T1D. However, the results are a bit unclear, as there was only a weak C-peptide preservation seen after Glucagon stimulation, but no effect at all after Mixed Meal Tolerance Test, and there was no differences whatsoever between the actively treated group and placebo in immune markers.

Active treatment with insulin has been shown not only to prevent or postpone diabetes in experimental animals but preliminary open studies indicated that such treatment could prevent diabetes in high risk individuals (10). Insulin, clearly a beta cell specific auto-antigen, has been parentally administrated (DPT) to prevent diabetes in high risk individuals with no effect, while oral insulin administration with the same purpose may have some effect (12).

1.1.4 Previous clinical studies with GAD-Alum (Diamyd)

GAD (Glutamic Acid Decarboxylase), can be regarded as an auto-antigen, as it is produced in the islets with increased release as response to beta cell stimulation. This protein has been shown to deeply influence the autoimmune immune process (31,32,33,34). Several studies have shown that indeed GAD can prevent diabetes in experimental animals (35-42). The observed effect, even after the start of the immune process, suggests that it might be possible to expect the same effect in humans after the start of the immune process.

1.1.4.1 GAD-Alum (Diamyd) vaccination

GAD-alum (Diamyd) therapy aims at intervening in the autoimmune process in T1D in order to preserve beta cell function and endogenous insulin secretion by modulating the immune system in a discrete, antigen-specific fashion to stop the destruction of beta cells. Thus, the goal of Diamyd therapy would be to dramatically slow or halt the ongoing autoimmune destruction of pancreatic islet beta cells in order to preserve the largest possible amount of endogenous insulin production.


1.1.4.2 Possible Reasons to the different results Phase II and Phase III

In Phase III randomization, patients receiving active drug were more often in the 10-11 year age group than in the 16-18 year age group whereas placebo was more frequent than active drug in the higher age group. This may have influenced the result. The Phase II patients were treated in March-April and those patients in Phase III who were treated in March-April had also significant effect of GAD-treatment. In the Phase II trial no vaccinations were accepted, but in Phase III Influenza-vaccination was allowed. Unfortunately an epidemic of H1N1-flu lead to that almost all patients were vaccinated, many of them in connection with the GAD-vaccinations. In Sweden and Finland the vaccine contained squalen, suspected to influence the immune system towards auto-immunity, and in these two countries there was no efficacy of GAD-treatment, while the efficacy was significant in other European countries. Patients in Sweden, who did not get the influenza vaccination close to the GAD-treatment, had better efficacy of GAD-treatment (46).

1.1.5. Vitamin D and type 1 diabetes

Experimental evidence indicates that vitamin D may play a role in the defence against T1D as well as type 2 diabetes (T2D). Epidemiological data suggest that there is a link between vitamin D deficiency and an increased incidence of T1D. Thus a multinational case-control study and a birth cohort follow-up study from Finland with (48,49) have both concluded that vitamin D3 supplementation at birth protects from T1D later in life, and a meta-analysis supports similar conclusions (50). Others report lower serum levels of 1α ,25-dihydroxyvitamin D3 [1,25(OH)2D3, calcitriol] in patients with recently diagnosed T1D than in healthy control subjects (51) The protective effects of vitamin D are mediated through the regulation of several components such as the immune system and calcium homeostasis. Thus, mechanistic studies show that 1,25(OH)2D3 modulates dendritic cell maturation in vitro and in vivo (52-55) and facilitates a shift from a Th1 to a Th2 immune response (56). An increasing amount of evidence suggests that vitamin D also affects beta cells directly thereby rendering them more resistant to cellular stress (57), and there are results indicating that vitamin D may also improve insulin sensitivity (58), which in turn decrease beta cell stress.

With this background vitamin D has been used in patients with recent onset T1D in an effort to preserve residual insulin secretion. However, so far Vitamin D alone has not been efficacious enough (59,60). Therefore there is reason to try Vitamin D, both in somewhat higher dose, and in combination with other therapy.

1.1.6 Etanercept and Type 1 diabetes

Although T1D is regarded to be an autoimmune disease, there are several studies both in experimental animals and in humans suggesting that an existing inflammation when autoantigen are presented to T-cells play an important role for which response the immune system will take.

We know that Tumor Necrosis Factor – α (TNF α) plays an important role for the destructive process in T1D. TNF α is involved in the autoimmune process leading to beta cell destruction (61,62). In the non-obese diabetic mouse, TNF α mRNA is produced by CD4+ T-cells within inflamed islets during the development of diabetes (63). In vitro models show that TNF α potentiates the direct functional inactivation and destruction of beta cells by other cytokines such as interleukin-1 β and interferon- γ (64-68). Transgenic mice with increased beta cell expression of TNF α have significant lymphocytic insulitis (69).

Etanercept is a recombinant soluble TNF α receptor fusion protein that binds to TNF α . It acts by clearing TNF α from the circulation, thereby blocking the biological activity of this inflammatory cytokine. Although etanercept is used in the treatment of many autoimmune diseases including ankylosing spondylitis, juvenile rheumatoid arthritis, psoriasis, psoriatic arthritis, and rheumatoid arthritis, (70,71) it has only been tested in young people with T1D (72). This was a 24-week double-blind, randomized, placebo-controlled study conducted at the Diabetes Center, Women and Children's Hospital of Buffalo. Eighteen subjects (11 male and 7 female, aged 7.8-18.2 years) were randomly assigned to receive either placebo or etanercept. The effect was quite impressive: The beta cell function was not only preserved but the percent change in C-peptide area under the curve from baseline to week 24 showed a 39% increase (!) in the etanercept group compared to a 20% decrease in the placebo group (P < 0.05). From baseline to week 24 insulin dose decreased 18% in the etanercept group compared with a 23% increase in the placebo group (P < 0.05). At the same time, with lower insulin dose, HbA1c at week 24 was lower in the etanercept group $(5.91 \pm 0.5\%)$ compared with that in the placebo group $(6.98 \pm 1.2\%)$; P < 0.05) with a higher percent decrease from baseline than in the placebo group (etanercept 0.41 + 0.1 vs. placebo 0.18+/- 0.21; P < 0.01). Seventeen patients completed the study, and none withdrew because of adverse events. In fact the adverse events were minimal in that study.

1.1.7 Rationale for etanercept and GAD-alum (Diamyd) in type 1 diabetes

There is consensus among diabetes researchers today that the key to curing T1D will be to simultaneously tackle the disease on several fronts by combining various therapeutics and that an autoantigen-specific treatment such as Diamyd will constitute an essential component in future combination therapies.

In this EDCR IIa trial, we propose that etanercept and GAD-alum will synergize in a novel manner to produce extended beta cell function in those newly diagnosed with T1D.

More specifically, although Phase III studies indicate GAD-alum alone does not preserve beta cell function enough, it does have a potent effect on the immune system. The data indicate that GAD-alum activates *both* TH2/immunoregulatory *and* TH1/proinflammatory components (73). Immunologically, TNF α plays an integral role in the initiation and progression of the innate and beta cell-specific autoimmunity (74). Blocking TNF α with etanercept in autoimmune patients has resulted in downregulation of Th1 and Th17 activation and an upregulation of Th2 and regulatory T-cell (Treg) subsets of immunocytes (75). If we can induce quiescence in the inflammatory immunologic milieu present in and around islets via combination treatment with etanercept, we could both *enhance* the TH2/immunoregulatory GAD-alum response *and* lessen the TH1/proinflammatory response.

Furthermore, metabolically, TNF α appears to inhibit insulin secretion, and acts in synergy with other cytokines such as IL1- β and IFN γ to enhance beta cell stress and destruction (74, 76, 77, 64). Experience with etanercept and other TNF α blockers in T1D animal models and clinical patients with T1D suggests that beta cell destruction can be arrested leading to better metabolic control (78, 79, 80, 81). Because it is a potent proinflammatory cytokine (74) blocking soluble TNF α (sTNF α) reduces the activation state of immunocytes (75), but additionally, because Etanercept preferentially binds sTNF α over membrane bound TNF α (mTNF α) expressed on Dendritic Cells (DC) (unlike other anti-TNF α agents), a DC-mediated antigen specific Treg generation is preserved (82, 83). By uniquely blocking B-cell borne Lymphotoxin- α , disrupting Follicular Dendritic cells and Germinal Center architecture in lymphoid tissue, anti-TNF α reduces B cell numbers and impairs activation (84), and autoantibody production should be reduced.

Preclinical data has shown that beta cell antigen delivered via quiescent DCs induce T-cell unresponsiveness and arrest beta cell destruction (85, 86).

We believe, therefore, that when etanercept therapy is added to GAD-alum treatment, GADspecific autoantibody levels and effector T cell activity and number will be reduced while GADspecific Treg number and function will be maintained. Due to its acute beta-cell-protective and metabolic effects, etanercept will also preserve beta cells directly. This will produce a deviation of the diabetes autoimmune response towards a regulatory phenotype of sufficient critical mass to lead to a significant and prolonged effect on beta cell preservation. This is not unlike the original rationale for the GAD-alum monotherapy approach evaluated in a number of clinical studies, but with critical improvements based on the knowledge gained from those trials.

1.1.8 Rationale for Vitamin D supplementation

As explained in the rational above, experimental evidence indicates that vitamin D may play a role in the defence against T1D and epidemiological data suggest that there is a link between vitamin D deficiency and an increased incidence of T1D. Mechanistic studies show that 1,25(OH)2D3 modulates dendritic cell maturation in vitro and in vivo (52-55) and facilitates a shift from a Th1 to a Th2 immune response (56). An increasing amount of evidence suggests that vitamin D also affects beta cells directly thereby rendering them more resistant to cellular stress (57), and there are results indicating that Vitamin D may also improve insulin sensitivity (58), which in turn decreases beta cell stress. Thus, there is reason to include Vitamin D in the combination with etanercept and Diamyd[®].

1.2 Summary

- The encouraging results of the Phase II GAD-alum trial and the partly positive results of the Phase III European Trial, support the concept that administration of GAD-alum (Diamyd) twice, at Day 1 and 30, may decrease the autoimmune process and contribute to preservation of residual insulin secretion
- Injection of GAD-alum (Diamyd) subcutaneously in the stomach area closer to pancreas and its neighbouring lymph nodes will likely increase the effect
- Addition of rather large doses of Vitamin D may improve the efficacy both via effects on the immune system and mechanism directly on the beta cells

• Treatment with etanercept, before and/or during treatment with GAD-alum will decrease the ongoing inflammation and improve/maintain the effect of GAD-alum treatment enforced by vitamin D.

With this background we believe that etanercept should be tried in combination with GAD-alum therapy and Vitamin D in rather large doses. Thus, we want to make an open pilot-trial where our first aim is to study safety, but then also elucidate efficacy and immunological mechanisms.

2 Risk-Benefit Analysis

2.1 Type 1 diabetes

The onset of human T1D is the clinical manifestation of beta-cell failure caused by T-cell mediated autoimmune destruction of the insulin producing pancreatic beta cells, a pathologic feature involving an inappropriate immunological recognition of the body's own tissues. This results in a life-long dependence on daily insulin injections and exposure to both the acute and late complications of T1D. T1D is a particular burden to children and their families, representing by far the most common chronic, serious, life-threatening disease in our country, and tends to become an extremely serious global problem.

By the time a T1D patient is diagnosed, up to 70-90% of pancreatic islet beta cell function has been lost due to autoimmune responses against specific beta cell antigens. Over time this autoimmune response persists and the amount of endogenous insulin that is produced is reduced. As this happens a T1D patient is reliant on exogenous insulin and is at greater risk for both short and long term complications of T1D. In the more acute manifestation of T1D, or in the absence of treatment, the lack of insulin can result in diabetic ketoacidosis (DKA), a potentially life-threatening medical emergency. Insulin therapy can dramatically reduce the possibility of death from DKA but even patients adequately treated with insulin are still at increased risk to a number of acute and long-term (chronic) complications. Acute complications include DKA and severe hypoglycaemia. Long-term complications of T1D include microvascular, macrovascular and neurologic complications that increase morbidity as well as mortality. Studies have shown that retained residual insulin production is associated with a reduction in DKA and hypoglycemic risk as well as in the development of long-term complications (6).

Although the use of insulin has dramatically improved the survival of patients with T1D, insulin does not represent a cure as individuals with the disorder, even if well managed, display marked increases in the frequency of debilitating and even life-threatening complications. The severity of these complications makes the development of a therapy allowing for beta cell preservation of great urgency for patients and caregivers. The world-wide incidence of T1D is increasing and despite the significant progress that has been made in its treatment, T1D still represents a severe burden on the individual and on society as well. Any intervention, which can stop or delay the complete loss of functional residual beta-cell mass would be significant as it would provide protection against hypoglycemia and provide improved metabolic control resulting in a delay and reduction in the micro and macro-vascular complications of diabetes.

In summary, T1D without residual insulin secretion is a dangerous disease with increased mortality in spite of a lifetime of intense treatment. There is currently no approved method or medicament to halt or slow the immune destruction of remaining pancreatic islet beta cells. Such a treatment would be of great benefit for all newly diagnosed T1D patients in the world, as well for the society.

In this new pilot-trial (EDCR IIa) it is proposed to use a treatment period with the TNF- α inhibitor etanercept of three months at a dose of 0.8 mg/kg body weight (max 50 mg) per week (as for children with JIA), in combination with Diamyd[®] at a dose of 20µg administered as a prime dose with a booster dose of 20µg one month later (2 doses of 20µg in total), and Vitamin D at a dose of 2000 IU per day during 15 months.

We argue that etanercept, Diamyd[®] and vitamin D in the proposed doses, and with the proposed exclusion and inclusion criteria, and careful follow-up are justified to try to stop the devastating progress of autoimmune beta cell destruction in new onset T1D, aiming to preserve blood glucose control and endogenous insulin secretion.

2.2 Risks of Diamyd[®]

Diamyd is an investigational experimental study drug (not marketed or approved) that has been studied in preclinical and clinical trials (Phase I through III). There are no risks of particular severity or seriousness anticipated based on the toxicological data in animals or prior studies in humans, except that patients have reported injection site reactions, such as e.g. itching, oedema, tenderness, bruises and pain. All patients recovered, and no patient was withdrawn from further treatment due to injection site reactions.

Theoretical risks of Diamyd[®] such as acceleration of the autoimmune process, undesirable effects on the immune system and neurological disease have been discussed and also thoroughly evaluated during several clinical trials in both children and adults, and all clinical studies performed with Diamyd[®] to date indicate a favorable safety profile for Diamyd[®] and no neurological concerns have been identified (see section 1.1.4 above and the Investigator's Brochure of Diamyd[®]). It is however possible that not yet detected side effects may be revealed in this or future clinical trials.

The dose of 20 µg of Diamyd[®], administered as a prime dose with a booster dose one month later or as a prime and boost on days 1 and 30 followed by one or two additional single doses (days 90 and 270) have been shown to be safe in man (children and adolescents) with few and mild adverse reactions. Recently approximately 60 patients have been randomized in the ongoing DIABGAD-1 trial and beside mild transient (a few hours) irritation at the injection site we have seen no adverse events related to the Diamyd treatment.

2.3 Risks of Etanercept (Enbrel[®])

Etanercept (Enbrel[®]) is one of the clinically most well-used biologics in the world and is regarded as justified in the treatment of Juvenile Idiopathic Arthritis (JIA) also in children down to 2 years of age.

Etanercept has documented side effects and the most commonly reported side effects are injection site reactions, infections (URI, bronchitis, cystitis and skin infections, reactivation of tuberculosis and other serious infections such as tuberculosis, and opportunistic infections, including invasive fungal infections, listeriosis and legionellosis), allergic reactions, development of autoantibodies, itching, pruritus and fever.

TNF blockers such as etanercept affect the immune system and its use can affect the body's immune response towards infections. Serious infections affect less than 1 of 100 patients that are treated with etanercept. Deadly and life-threatening infections as well as sepsis have been reported. Different kinds of malignancies have also been reported while treated with etanercept,

even if this AE has been questioned by Swedish researchers as the incidence of malignancy in children and adults with rheumatic disorders is increased even without treatment. Additionally hematological, neurological and autoimmune reactions have been reported, including rare cases of pancytopenia (less than 1 of 1000) and very rare cases of aplastic anemia (less than one of 10 000). Central and peripheral demyelination has been reported in both rare and very rare cases. Also, rare cases of lupus and lupus-like syndrome and vasculitis have been reported

There are also reports that the risk for hypoglycemia may increase in patients with diabetes being treated with etanercept.

2.4 Risks of Vitamin D supplementation

There are no anticipated risks of vitamin D supplementation at the dose to be administered in this study, although toxic levels may induce hypercalcemia with symptoms such as tiredness, euphoria, nausea, drowsiness, weight loss, thirst, polyuria, nefrocalcinosis and renal failure. Additional symptoms of vitamin D toxicity include ECG changes, arrhythmia and pancreatitis.

In DIABGAD-1 we give vitamin D 2000 IU per day for 15 months. This dose given to children and adolescents aged 10-18 years can be compared with the dose of 400 IU per day given to babies as a health recommendation to avoid vitamin D insufficiency. Approximately 60 patients in DIABGAD-1 have been randomized of whom ³/₄ should have received Vitamin D, and we have noticed no adverse event which can be regarded as related to Vitamin D.

Vitamin D in a dose of 2000 IU/day in children has been reported safe (87). Additionally, a dose of up to 7000 IU/day to children from 5 years of age with HIV did not raise any safety concerns (88).

However, as an extra safety measure, vitamin D serum levels and Calcium will be analyzed at most visits. Patients will only be included in the trial if their baseline Vitamin D is below 100 nmol/L and the Vitamin D treatment will be dismissed if Vitamin D levels are above 125 nmol/L or if the patient develops hypercalcemia. Vitamin D treatment will be started again if the levels fall <100 nmol/L.

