4.2 Endpoints

4.2.1 Primary endpoints

Primary endpoints:

To Evaluate the tolerability of a combination therapy with Diamyd, Vitamin D and etanercept at Month 6 (main study Period), 9, 15 and 30 (extension study period)

Variables to evaluate tolerability:

- Reactions of the injection site
- Infections
- Occurrence of Adverse Events (AEs)
- Occurrence of Serious Adverse Events
- Physiological and Neurology assessments
- Laboratory measurments (biochemistry and haematology), including Calcium and Vitamin D in serum
- GAD65AB titer (GADA)

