6.2 Assessments and Procedures

- 1. Standard insulin treatment, education and psychosocial support for newly diagnosed T1D patients.
- 2. Normalization of fluid, electrolyte and acid-base balance.
- 3. Thereafter information about the study.
- 4. When the patients and parent(s) / legal guardian(s) have given their informed consent, at the latest 100 days after diagnosis, screening is performed with a fasting venous sample from patients who are eligible according to other criteria than C-peptide and GADA concentrations (Visit 1). Patients are also tested for tuberculosis, renal or liver disease at this visit (see section 5.3.1 and 5.3.2 above).
- 5. At Visit 2 (Baseline), Visit 6 (6 months), Visit 8 (15 months) and Visit 9 (30 months), assessment of residual endogenous insulin secretion by MMTT.
- 6. Blood sampling for Vitamin D in serum at Visit 1, and then after one month of treatment at Visit 3 (before the first GAD-alum treatment) and at Visit 8 (15 months)
- 7. HbA1c, safety (haematology and chemistry), autoantibody titres (GAD65, IA-2), immunology are followed by blood samples at every visit.
- 8. Exogenous insulin dose/24 hours, AEs and concomitant medication are registered at every visit.
- 9. Self-reported hypoglycaemia (defined as needing help from others and/or seizures and/or unconscious) registered at every Study Visit.
- 10. Any symptoms or signs of other medical problems should be treated at the discretion of the clinical doctor. Thus if a patient experiences symptoms and/or signs of infection that should be treated lege artis.

Examinations will be performed according to table 2 in Section 7 below, and in the order outlined in the case report form (CRF).

6.2.1 All Visits, Visit 1 through 9

Note that the patient should attend all study visits in the morning following an overnight fast (> 10 hours, water allowed).

For patients with evidence of an infection (including fever), the complete visit should be postponed for 5 days or until the patient has recovered.

6.2.2 Injections with GAD-Alum (Diamyd), Visits 3 and 4

Injections of GAD-alum (Diamyd) will be administered at Visits 3 and 4, subcutaneously in the stomach area.

After the injection, the patient shall remain in the vicinity of the study site for the next hour, and the injection site will be examined by investigator/study nurse 1 hour post injection.

6.2.3 Mixed Meal Tolerance Test (MMTT), Visits 2, 6, 8 and 9

The MMTT must be performed according to the instructions in the CRF.

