6.7.2 General precautions during Vitamin D treatment

Blood draws for Vitamin D will be taken at screening (Visit 1), month 1 (Visit 3), month 6 (Visit 6), month 9 (Visit 7) and month 15 (Visit 8) and be analyzed continuously. Blood draws for Calcium will be taken at every visit. Should the blood concentration during Vitamin D treatment exceed 125 nmol/L or if the child would develop hypercalcemia, the Vitamin D treatment will be stopped. The subject will however continue in the study and complete all the other study related evaluations, including sampling for Vitamin D and Calcium levels.

Vitamin D treatment will be started again if the levels fall <100 nmol/L.

Vitamin D treatment will be stopped and not started again if the subject develops hypercalcemia.

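### Section 2.4 allows vitamin D to restart without the bar after hypercalcemia that 6.7.2 sets, and the draw list in 6.2 omits the Month 6 and Month 9 levels that the stop and restart rule needs

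*Combined protocol and SAP*

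**What the plan says.** **Stop and restart.** Section 2.4 gives two reasons to stop: "the Vitamin D treatment will be dismissed if Vitamin D levels are above 125 nmol/L or if the patient develops hypercalcemia". The sentence after it reads "Vitamin D treatment will be started again if the levels fall <100 nmol/L", with no condition on why treatment was stopped. Section 6.7.2 has the same two reasons to stop and the same restart sentence, but then adds "Vitamin D treatment will be stopped and not started again if the subject develops hypercalcemia".

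**Vitamin D draws.** Section 6.2 item 6 takes these samples "in serum at Visit 1, and then after one month of treatment at Visit 3 (before the first GAD-alum treatment) and at Visit 8", where the last is Month 15. Section 6.7.2 has a longer list: "Blood draws for Vitamin D will be taken at screening (Visit 1), month 1 (Visit 3), month 6 (Visit 6), month 9 (Visit 7". Month 15 (Visit 8) follows in the same sentence. Section 2.4 says only that "vitamin D serum levels and Calcium will be analyzed at most visits".

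**Use of the values.** Section 4.2.1 names laboratory measurements, "including Calcium and Vitamin D in serum", among the variables for evaluating tolerability. Months 6 and 9 are among its time points.

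**Dosing.** Sections 8.1 and 8.3 give vitamin D daily from Day 1 to Day 450.

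**The concern.** Two sections that a site may consult give different instructions for the same child. If a child has had hypercalcemia and the vitamin D level later falls below 100 nmol/L, 2.4 read as written restarts treatment and 6.7.2 forbids it.

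The 125 and 100 nmol/L thresholds can act only on a measured level. If a site takes its draws from 6.2 item 6, a rise above 125 nmol/L after Day 30 would not show on a scheduled sample until dosing ends, and a child stopped at Day 30 would have no scheduled level on which to restart. The same site would have no Month 6 or Month 9 vitamin D value to summarize. With about 20 children and a purely descriptive analysis, values not collected at some sites cannot be made good later.

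**Working it through.** The plan states no figure of its own on this point. The check sets the sections side by side and counts days between draws at the nominal visit days in Table 1: Visit 3 is Day 30, Visit 6 is Day 180, Visit 7 is Day 270 and Visit 8 is Day 450.

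**1. Restart rule**

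| Situation | 2.4 | 6.7.2 |
|---|---|---|
| Level above 125 nmol/L | stop | stop |
| Hypercalcemia | stop | stop |
| Level later below 100 nmol/L, stopped for a high level | restart | restart |
| Level later below 100 nmol/L, stopped for hypercalcemia | restart (no exception given) | no restart |

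The sections agree on three rows and conflict on the fourth.

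**2. Draws after the start of dosing**

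- 6.2 item 6: Days 30 and 450. Gap = 450 − 30 = 420 days; 420/450 = 93.3% of the treatment period.
- 6.7.2: Days 30, 180, 270 and 450. Gaps = 180 − 30 = 150, 270 − 180 = 90 and 450 − 270 = 180 days. Longest = 180 days; 180/450 = 40.0%.
- Draws while dosing still has time to run (before Day 450): 1 under item 6 (Day 30) and 3 under 6.7.2 (Days 30, 180 and 270).
- Scheduled levels on which a child stopped at Day 30 could restart before Day 450: none under item 6, two under 6.7.2 (Days 180 and 270).

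**3. Fit with 2.4.** Item 6 covers 3 of the 9 visits and 6.7.2 covers 5 of 9. Only the 6.7.2 list is a majority of visits, as 2.4 describes.

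**4. Tolerability variable.** At Months 6 and 9, 6.7.2 supplies a vitamin D value and item 6 does not. At Month 15 both do.

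**5. Assays needed to bring item 6 up to 6.7.2.** Two further draws (Visits 6 and 7) × about 20 children = about 40.

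**The case against.** The strongest reply is that 2.4 is a risk summary and 6.7.2 is the operative section. In 2.4 the restart sentence speaks of levels falling, so it can be read as answering only the level-based stop. That is a fair reading, and it makes 2.4 an abridgement more than a rival instruction. Still, the sentence directly follows one that names both reasons to stop, and nothing in it separates them.

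On the draws, 6.2 sends sites to Table 2 for the examinations. The end of that table is damaged in the available text. The surviving marks, one at Visit 1 and extra ones at Visits 3, 6, 7 and 8, fit the 6.7.2 schedule, but the row label is lost, so this is supportive only. The damage is not a fault of the plan. If the table does follow 6.7.2, item 6 is a drafting slip that a site using the table would not feel. The 420-day gap applies only to a site that works from item 6.

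Four stronger readings are tempting and are not supported:

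- **Months of further vitamin D after hypercalcemia.** A reader might count the days from a restart at Day 180 or Day 270 to the end of dosing. That takes the restart from 2.4 and the draw from 6.7.2. A site using 6.7.2 for its draws has the bar in the same short section, and a site using item 6 has no scheduled level before Day 450 on which to restart.
- **A missing Month 30 level.** Section 4.2.1 lists variables and time points together and does not promise every variable at every time point. Injection-site inspection, for example, appears in Table 2 only at Visits 3 and 4. Dosing ends at Day 450, so having no later level is reasonable.
- **A further conflict in 5.4.** Stopping on symptoms of hypercalcemia is an additional, more cautious trigger. That 5.4 does not refer to the restart rule is not a contradiction.
- **Hypercalcemia going unseen.** Calcium is drawn at every visit under 6.7.2 and Table 2, so its detection does not depend on the vitamin D draws.

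**Conclusion.** Two wording conflicts stand: the unqualified restart in 2.4 against the bar in 6.7.2, and the three-visit draw list in 6.2 item 6 against the five-visit list in 6.7.2. For a site that follows item 6, no vitamin D level is scheduled for 420 of 450 treatment days, against a longest gap of 180 days under 6.7.2, and the Month 6 and Month 9 values are lost.

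The point is minor. Both sections stop treatment on hypercalcemia, 6.7.2 is specific and complete, calcium is followed at every visit, and adverse event counts are not affected. The day counts use nominal visit days and scheduled samples only, and assume no rate of hypercalcemia or of high levels. Two things remain unknown: what the vitamin D row of Table 2 shows, and what the separate Safety Plan says, since it is not among the documents. Either may already give sites the right rule, but neither would make these protocol sections agree.

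**What to change.** - **Section 2.4:** limit the restart sentence to treatment stopped for a level above 125 nmol/L and add that vitamin D is not restarted after hypercalcemia. Alternatively, replace the sentence with a reference to 6.7.2.
- **Section 6.2 item 6:** list vitamin D draws at Visits 1, 3, 6, 7 and 8, as in 6.7.2.

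Sections 4.2.1, 5.4 and 6.7.2 can stay as they are. In particular, the symptom stop in 5.4 should not become a hold with resumption when calcium is normal. That item includes nephrocalcinosis and renal failure, and such a rule could let an affected child resume.

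The cost is two wording edits. Against 6.7.2 there are no added draws. Against item 6 there are two more assays per child, about 40 in all, at visits where blood is already taken.
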